5.4. Screen Failures

Screen failures are defined as participants who consent to participate in the clinical study but are not subsequently randomly assigned to study intervention. A minimal set of screen failure information is required to ensure transparent reporting of screen failure participants to meet the Consolidated Standards of Reporting Trials publishing requirements and to respond to queries from regulatory authorities. Minimal information includes demography, screen failure details, eligibility criteria, and any applicable SAE (see [Section 8.4.1](#)).

Individuals who do not meet the criteria for participation in this study (screen failure) may be rescreened once if the rescreening is approved by the Sponsor Medical Monitor. Rescreened participants should be assigned a new participant number.

5.5. Criteria for Temporarily Delaying Administration of Study Intervention

As indicated in [Section 6.5](#), dose modifications are not permitted during the Maintenance Period. See [Section 7.1.3](#) for details regarding temporary interruption of study intervention.

6. STUDY INTERVENTIONS AND CONCOMITANT THERAPY

Study intervention is defined as any investigational intervention(s), marketed product(s), or placebo intended to be administered to a study participant according to the study protocol.

6.1. Study Interventions Administered

The study interventions planned for use in this study are described in [Table 7](#).

Table 7: Study Interventions

Treatment Arm	Intervention/Treatment Name ^a	Formulation	Unit Dose Strength(s) ^b	Dosage Level(s)	Route of Admin.	Use	Sourcing	Package	Labeling	Storage Conditions
■										
■										

Treatment Arm	Intervention/ Treatment Name ^a	Formulation	Unit Dose Strength(s) ^b	Dosage Level(s)	Route of Admin.	Use	Sourcing	Package	Labeling	Storage Conditions
			[REDACTED] [REDACTED]	[REDACTED] [REDACTED]						

Abbreviations: admin = administration; [REDACTED]
[REDACTED] QD = once daily.

^b The dose strength of suvaceftamide is based on the active moiety in the drug product.

6.2. Preparation/Handling/Storage/Accountability

1. Further guidance and information for the final disposition of unused study intervention are provided in the Trial Site Binder.
2. The investigator or designee must confirm appropriate temperature conditions have been maintained during transit for all study intervention received and any discrepancies are reported and resolved before use of the study intervention.
3. Only participants enrolled in the study may dose with study intervention.
4. At clinic visits, only authorized site staff may dispense or administer study intervention.
5. All study intervention must be stored in a secure, environmentally controlled, and monitored (manual or automated) area in accordance with the labeled storage conditions with access limited to the investigator and authorized site staff.
6. The investigator, institution, or the head of the medical institution (where applicable) is responsible for study intervention accountability, reconciliation, and record maintenance (ie, receipt, reconciliation, and final disposition records). Refer to the Pharmacy Manual for details.

6.3. Measures to Minimize Bias: Randomization and Blinding

All participants who sign the ICF will receive a participant number by IRT at Screening. The participant number identifies the participant for all study procedures that occur throughout the study. This number is unique and once assigned, cannot be reassigned to another study participant.

Treatment allocation/randomization for this study will occur centrally through the use of an IRT. Participants eligible for the study will be randomized in a 1:1 ratio to receive once-daily doses of suvecaltamide or placebo. Randomization will be stratified by the TETRAS composite outcome score (≤ 17 or > 17) as assessed at Baseline. A double-blind approach will be used throughout the 17-week treatment period (ie, during the Dose Titration and Optimization Period as well as the Maintenance Period). During the Dose Titration and Optimization Period the number of capsules of suvecaltamide or placebo taken each day will be titrated based on efficacy response and tolerability. Participants will enter the Maintenance Period on 1, 2, or 3 capsules of either suvecaltamide (10 mg per capsule) or placebo. Suvecaltamide and placebo capsules will appear identical.

The IRT will be programmed with blind-breaking instructions. In case of an emergency, the investigator has the sole responsibility for determining if unblinding of a participants' intervention assignment is warranted. Participant safety must always be the first consideration in making such a determination. If the investigator decides that unblinding is warranted, the investigator should make every effort to contact the sponsor prior to unblinding a participant's intervention assignment unless this could delay emergency treatment of the participant.

If a participant's intervention assignment is unblinded, the sponsor must be notified within 24 hours after breaking the blind. The date and reason that the blind was broken must be recorded in the source documentation and IRT system, as applicable. The participant's treatment assignment may be unblinded for regulatory reporting purposes. Notification of the treatment

assignment is only made known to those who require it for safety reporting and submission processes. All other individuals involved in the study, including the investigator, will remain blinded to treatment assignment. Participants for whom the blind is broken for this reason will not be withdrawn from the study. Sponsor safety staff may unblind the intervention assignment for any participant with an SAE. If the SAE requires that an expedited regulatory report be sent to one or more regulatory agencies, a copy of the report, identifying the participant's intervention assignment, may be sent to investigators in accordance with local regulations and/or sponsor policy.

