5.1. Inclusion Criteria

Participants are eligible to be included in the study only if all of the following criteria apply:

1. Male and female participants ages 40 to 85 years inclusive, at time of signing the ICF.
2. Body mass index from 17 to 45 kg/m² (inclusive) at Screening.
3. Diagnosis of clinically probable or clinically established PD meeting the MDS 2015 criteria ([Postuma, 2015](#)).
4. Participants must be individually optimized on PD medications for the treatment of other cardinal signs of PD (bradykinesia, rigidity) per the judgement of the investigator.
Optimized treatment is defined as the maximum therapeutic effect obtained with PD medications when no further improvement is expected regardless of any additional adjustments to these medications or when the PD medications or adjustments to these medications are anticipated to result in intolerable side effects. This will be based on the investigator's clinical judgement.
5. Participants must be on a stable dosing regimen of their permitted PD and/or other tremor (eg, propranolol) medications for the treatment of motor symptoms for at least 6 weeks prior to Screening and do not anticipate the need to make any changes for the duration of the study. A lack of use of medications used to treat motor symptoms also must be stable for 6 weeks prior to Screening and remain stable for the duration of the study (eg, participants who tried PD medications and are no longer taking them must be off of these medications and stable for 6 weeks prior to Screening).
6. For participants who experience motor fluctuations, tremor must also be present during "ON" periods and participants should be able to have tremor symptoms evaluated during "ON" periods, as determined by the investigator, in relation to the participant's PD medications. If necessary, participants may take their PD medications in the clinic during visits where tremor symptoms are evaluated (timing of PD medications relative to tremor evaluations can be determined by the investigator).
7. Participants have moderate to severe impairment associated with tremor at both the Screening and Baseline Visits, as determined by all the following:
 - a. A score of > 21 on the TETRAS-ADL subscale; and
 - b. This criterion has been removed.
 - c. CGI-S rating of tremor severity of > 2 (at least moderate for participants ability to function).

8. Contraception:

a. Male participants:

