9.4.2. Primary Estimand

The attributes of the primary estimand are listed in [Section 3](#).

For the main estimator analysis, a MMRM will be used to include the change in the TETRAS composite outcome score from Baseline to Weeks 5, 9, 13, and 17. The model will include treatment group, visit, treatment-by-visit interaction, baseline-by-visit interaction, and randomization stratum as fixed effects; baseline TETRAS composite outcome scores as a covariate; and week repeated within each participant as repeated effect. An unstructured variance-covariance matrix will be used to model the correlation among repeated measurements. The Kenward-Roger adjustment of degrees of freedom along with REML will be used to make proper statistical inference. Within-group LS means and the associated 2-sided 95% CIs, treatment difference in LS means and associated 2-sided 95% CIs and p-values will be reported.

Per the treatment policy, the main analyses will include data collected during the Efficacy Follow-up Visits for participants who experience ICEs. However, for participants who experience ICEs and do not attend Efficacy Follow-up Visit(s), missing data will be handled per [Section 9.4.1.5](#).

For sensitivity analysis, control-based imputation methods ([Roger, 2012](#)) will be used to handle missing observations in addition to treatment policy. Details will be further defined in SAP.

For supplementary analysis, a hypothetical strategy will be used to include data points up to the timepoint when a participant experiences an ICE into the MMRM specified above. This will serve as complementary analysis and will ignore observations collected after an ICE.

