#### 4.1.1. Definitions

##### 4.1.1.1. Baseline

Baseline is defined as the last evaluation taken prior to the date of first dose of study intervention. This value may be obtained at Baseline or during the screening period. If there are multiple valid observations prior to the first dose, then the latest non-missing observation prior to the date of first dose of study intervention will be used as the baseline in the analysis.

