#### 4.1.2. Visit Windows

All scheduled, unscheduled, and early discontinuation study visits will be summarized based on derived analysis visit window mapping rule outlined per Table 7, which may or may not be the same visit recorded in the database.

For assessments conducted in triplicates, the average value should be mapped. For the Screening visit, the latest assessment conducted prior to Baseline will be used.

If multiple assessments are recorded within a single visit window (including scheduled, unscheduled, repeated, and retest assessments or measurements as well as early discontinuation data), the scheduled assessment should always be prioritized to be mapped to the analysis visit. If there is more than 1 scheduled visit, the following rules can be used to decide which assessment will be mapped to the analysis visit:

- If 2 or more observations occur within the same visit window, then the non-missing observation closest to the scheduled visit day will be used in the analysis.
- If 2 observations are equidistant from the scheduled visit day, then the non-missing observation with the earliest collection date will be used in the analysis.
- If 2 observations are collected on the same day, then the non-missing observation with the earliest collection time will be included in the analysis.

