### 4.2.2. Main Analytical Approach

The analysis will be conducted under the treatment policy framework using the Full Analysis Set.

For the main estimator analysis, a MMRM specified below will be used to analyze the change of the TETRAS composite outcome score from Baseline to Weeks 5, 9, 13 and 17.

$$dTCOM_{ij} = \alpha_{j(i)} + \beta_1 * baseTCOM_i + \beta_2 * week_j + \beta_3 * treatment_i + \beta_4 * treatment_i * week_j + \beta_5 * baseTCOM_i * week_j + \beta_6 * stratum_i + \varepsilon_{ij}$$

The model will include treatment group ( $treatment_i$ ), study visit ( $week_j$ ), treatment-by-visit interaction ( $treatment_i * week_j$ ), baseline-by-visit interaction ( $baseTCOM_i * week_j$ ), and randomization stratum ( $stratum_i$ ) as fixed effects, baseline TETRAS composite outcome score ( $baseTCOM_i$ ) as a covariate, and week repeated within each participant as repeated effect ( $\alpha_{j(i)}$ ).

An unstructured variance-covariance matrix will be used to model the correlation among repeated measures. If the model fails to converge on the Newton-Raphson Algorithm, the alternative Fisher scoring algorithm should be explored before considering other variance-covariance structures.

The Kenward-Roger's adjustment of degrees of freedom along with restricted maximum-likelihood (REML) computation method will be used. Least square mean (LS mean) and standard error (SE) at Weeks 9, 13 and 17 will be provided and graphed in a line plot for both treatment groups. The LS mean difference between JZP385 and placebo at Weeks 9, 13 and 17, along with the 2-sided 95% confidence interval (CI) and associated p-value will be provided.

Treatment dropouts and missing observations for the main analytic approach will be handled according to Section 4.1.4.

An example SAS code for MMRM analysis is as follows:

```
PROC MIXED DATA=INDATA METHOD=REML;
```

```
CLASS SUBJECT TRT WEEK STRATUM;
MODEL CHG = BASELINE TRT WEEK STRATUM TRT*WEEK BASELINE*WEEK /
RESIDUAL OUTP=RESIDUAL DDFM=KR;
REPEATED WEEK/TYPE=UN SUB=SUBJECT;
LSMEANS TRT*WEEK / CL DIFF ALPHA=0.05;
RUN;
```

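### The TETRAS composite is rated at Screening as well as at Baseline, but the TETRAS MMRMs adjust only for the Baseline value, so a modest gain in precision goes unused.

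*Protocol*

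**What the plan says.** - **Collection.** In the Schedule of Activities (Protocol Table 4), both TETRAS subscales are marked at Screening and at Baseline. Inclusion criterion 7 uses both visits for eligibility: "Participants have moderate to severe impairment associated with tremor at both the Screening and Baseline Visits".
- **Stratum.** Protocol 6.3 bases it on the Baseline composite: "Randomization will be stratified by the TETRAS composite outcome score (≤ 17 or > 17) as assessed at Baseline".
- **Primary model.** Protocol 9.4.2 lists "baseline TETRAS composite outcome scores as a covariate". The SAP 4.2.2 code reads "MODEL CHG = BASELINE TRT WEEK STRATUM TRT*WEEK BASELINE*WEEK" and has no Screening term. SAP 4.4.1 gives the three unmodified TETRAS scores the same structure.
- **Definition of baseline.** SAP 4.1.1.1 takes one value: "the latest non-missing observation prior to the date of first dose of study intervention will be used as the baseline in the analysis". It adds that "This value may be obtained at Baseline or during the screening period", so Screening enters the efficacy models only when the Baseline rating is missing.
- **Availability.** SAP 4.1.2 already derives a Screening value: "For the Screening visit, the latest assessment conducted prior to Baseline will be used".

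Neither document gives the Screening score any other role in the efficacy models or explains why it is left out.

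**The concern.** The composite is a 14-item rated score and will vary from visit to visit for reasons unrelated to true severity. A single Baseline rating is therefore an imperfect covariate. A second rating taken before randomisation helps to separate true severity from rating noise and so reduces the unexplained variance at Week 17. Because it precedes randomisation, adjusting for it does not bias the treatment comparison and leaves the endpoint and the estimand unchanged.

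The stake is power on the primary test. The trial is sized at 80%, and under the fixed sequence (Protocol 9.4.1.1, SAP 2.1) failure on the primary stops formal testing of the CGI-S. The unmodified TETRAS-ADL, TETRAS-PS and TETRAS total analyses would gain in the same way.

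**Working it through.** **1. The plan's own figure.** SAP 5 uses a difference of 3.0, SD 6.0, 64 evaluable per arm and a two-sided 0.05 two-sample t-test. The non-central t gives 80.1% power at 64 per arm and 79.5% at 63. Then 64 / 0.80 = 80 per arm, or 160 in all. The figure is reproduced. It takes no credit for any covariate.

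**2. Variance model.** The only variance input in the documents is the change SD of 6.0; the rest is assumed.
- Baseline = T + e and Week 17 = T + individual change + e. T has SD τ (4 to 6), each rating error has SD σ (1.5 to 3), and individual change has variance γ² = 36 − 2σ².
- Baseline only: V1 = τ²σ²/(τ² + σ²) + γ² + σ².
- Screening added: V2 = 1/[1/τ² + 1/σ² + 1/(σ² + δ²)] + γ² + σ². Here δ is the SD of real drift between Screening and Baseline, and δ = 0 makes the two ratings replicates. In that case their correlation runs from 0.64 to 0.94 over the grid.

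With Baseline in the model, analysing change or the Week 17 score gives the same treatment contrast, so V1 and V2 are the relevant residual variances.

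**3. One case in full (τ = 5, σ = 2.5).** γ² = 36 − 12.5 = 23.5.
- V1 = 25 × 6.25/31.25 + 23.5 + 6.25 = 5.00 + 29.75 = 34.75.
- δ = 0: V2 = 1/(0.04 + 0.16 + 0.16) + 29.75 = 2.78 + 29.75 = 32.53.
- δ = 3: V2 = 1/(0.04 + 0.16 + 1/15.25) + 29.75 = 3.77 + 29.75 = 33.52.

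**4. Results.** Power is for 3.0 points at 64 per arm, from the non-central t.

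| τ, σ | Baseline only: V1, power | Screening added, δ = 0 | Screening added, δ = 3 |
|---|---|---|---|
| 4, 1.5 | 35.72, 80.4% | 34.80 (−2.6%), 81.4% | 35.43 (−0.8%), 80.8% |
| 5, 2.5 | 34.75, 81.5% | 32.53 (−6.4%), 84.0% | 33.52 (−3.6%), 82.9% |
| 6, 3 | 34.20, 82.1% | 31.00 (−9.4%), 85.6% | 32.14 (−6.0%), 84.4% |

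Over the whole grid:
- **Replicates:** variance falls 2.6% to 9.4% and power rises 1.0 to 3.5 points. In participants this is 160 × (1/0.974 − 1) = 4 to 160 × (1/0.906 − 1) = 17.
- **Drift SD 3:** variance falls 0.8% to 6.0% and power rises 0.3 to 2.3 points. This is worth 160 × (1/0.992 − 1) = 1 to 160 × (1/0.940 − 1) = 10 participants.

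**5. Checks.**
- Simulated ANCOVA (τ 5, σ 2.5, replicates; 6,000 trials) gave power of 81.6% against 83.8%. With eligibility truncation at both visits it gave 81.9% against 83.9%. Type I error was 5.0% against 5.2% (Monte Carlo SE 0.3).
- If Screening is related to Week 17 only through Baseline, the residual variance does not change. At a Baseline–Week 17 correlation of 0.6 and a Screening–Baseline correlation of 0.8 it is 0.64 with or without Screening.
- Setting all pairwise correlations equal at 0.6 is more favourable: the variance ratio is 0.86, or about 0.89 to 0.92 after truncation at both visits. That pattern treats all of the change SD as visit noise, so it is an optimistic bound.

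**6. The stratum.** With N = 128 and all correlations 0.6, the simulated SD of the estimate is 0.142 with the stratum on Baseline and 0.141 with it on the mean of the two ratings, Screening being absent from the model in both. With the Baseline stratum kept and Screening added to the model it is 0.132. The gain comes from the model.

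**The case against.** The strongest reply is that nothing here is wrong. The MMRM adjusts for baseline, baseline-by-visit and stratum, which is a sound specification. The sample size was set without covariate credit, so baseline adjustment already adds margin. Leaving out a second, correlated severity measure contradicts nothing in the documents. All of this stands.

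The second reply is that the two ratings are not replicates. Table 4 allows Screening up to 28 days before the first dose. Protocol 4.1 and section 8 have prohibited medications washed out in between, and Screening is the only fasted visit (5.3.1). Section 8 also asks for the same rater throughout where possible, which may reduce the noise from which the gain arises. This stands too, and it is why the drift scenario and the zero case belong in the range.

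The third reply is that one extra term in SAP 4.2.2 is not the whole job. The control-based and tipping-point analyses (SAP 4.2.4.1 and 4.2.4.2) refit that MMRM on data imputed without Screening, and the subgroup analyses (SAP 4.2.3) inherit it. This is correct and is met in the fix.

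A reader might infer from Protocol 6.3 that stratifying on a single rating itself wastes precision. The documents and the check in step 6 do not support that: with the composite also in the model, moving the stratum to the mean of the ratings changes almost nothing.

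**Conclusion.** This is a missed efficiency and an inexpensive improvement. A score that is already collected before randomisation is left out of the TETRAS models. The likely return is about 3% to 9% of residual variance (1 to 3.5 power points) if the ratings behave as replicates, about 1% to 6% (0.3 to 2.3 points) with real drift of SD 3, and nothing if Screening carries no information beyond Baseline. Apart from the change SD of 6.0, every input is assumed, because the documents report no test-retest SD or correlation for the composite in Parkinson's disease. Protocol 8.2 itself says that TETRAS has not been validated in that population.

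It should not be read as showing that the trial is underpowered or the primary analysis invalid: the 80% at 64 per arm reproduces, and the planned model is unbiased without Screening.

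**What to change.** Amend the SAP before unblinding and list the change in SAP 4.9.

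- **Primary model (SAP 4.2.2).** Keep change from Baseline as the response. Add the Screening composite and its interaction with visit (SCREEN and SCREEN*WEEK) as separate terms. Do not average it with Baseline: washout and up to 28 days separate the ratings, and a separate term lets the data set its weight.
- **Unmodified TETRAS models (SAP 4.4.1).** Add the matching Screening score to each. SAP 4.4.3 and 4.5.2 borrow this model for other scales, so state that the terms apply to TETRAS scores only; Table 4 does not schedule the MDS-UPDRS at Screening.
- **Missing Screening score.** Fill it with the pooled mean, ignoring arm, so that no participant is dropped.
- **Imputation (SAP 4.2.4.1 and 4.2.4.2).** Add Screening to the imputation models so that they match the analysis model.
- **Subgroups (SAP 4.2.3).** Allow the Screening terms to be dropped where data are sparse.
- **Stratum.** No change.

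The cost is four extra model parameters (one main effect and three interaction terms for four visits), some collinearity with Baseline, and an amendment to a SAP already issued as final V1.0. Protocol 9.4.2 can be aligned, which under Protocol 10.1.1 requires ethics and, as applicable, regulatory approval, or the difference can be recorded in SAP 4.9. No new visits, data or participants are needed.

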6.4. Study Intervention/Treatment Compliance

For clinic visits where participants are dosed at the site (ie, during Weeks 1, 9, 13, and 17), participants will receive study intervention directly from the investigator or designee, under medical supervision. The date and time of each dose of study intervention administered in the clinic will be recorded in the source documents. In addition, the time of last meal and last dose of study intervention taken prior to the clinic dose will be recorded in the source documents. The dose of study intervention and study participant identification should be confirmed at the time of dosing by a member of the study site staff other than the person administering the study intervention. Study site staff will examine each participant's mouth to ensure that the study intervention was ingested.

For clinic visits where participants dose at home (ie, during Weeks 2, and 5), participants will self-administer study intervention at home and compliance with study intervention will be assessed at each clinic visit. The date and time of the dose of study intervention on the day of the clinic visit will be recorded in the source documents. Compliance will be assessed by direct questioning and counting returned capsules during the clinic visits and documented in the source documents. Deviation(s) from the prescribed dosage regimen should be recorded.

A record of the quantity of suvecaltamide (or placebo) capsules dispensed to and administered by each participant must be maintained and reconciled with study intervention and compliance records. Intervention start and stop dates, including dates for intervention delays (see [Section 7.1.3](#)) should also be recorded as applicable.

